Date: April 9, 2019

Title: Importance of Sock Type in the Development of Foot Lesions on Low-difficulty, Short Hikes.

Description of document: Materials and Methods (Study Protocol: description of the clinical study, including objective and design. Statistical Analysis Plan (description of the statistical considerations for analyzing the data collected in the study.) results of the study (Results obtained in the study) and Supplementary data (protocol of measures and other tables).

Materials and Methods

1. Permission and participants

All participants signed an informed consent form, and permission for the study was obtained from the Bioethics Committee (reference 126/2016). The admission criteria were: be of legal age, have no current health problems that would hinder or prevent participation in the hike, and carry a backpack weighing less than 3 kg. Participants were asked to use specific hiking footwear (light, flexible, soft-soled, with good grip and breathable material) (low top hiking shoes), based on earlier studies [38-40]. They were also asked to do the entire hike following the instructions of an experienced guide and to not remove their footwear or socks before examination by a podiatrist.

2. Sock type and interventions performed

Socks were of two types: technical socks, designed for high performance sports use (Lurbel brand, models Tierra and Set), and non-technical socks for everyday use. The socks had different composition: Tierra (50% regeneractiv, 25% cool-teak, 17% polyamide ions, 8% lycra); Set (75% cotton, 17% polyamide, 8% lycra) and cotton (98% cotton, 2% elastane). The technical socks had reinforced weave in the toe, metatarsal and heel areas.

Participants were examined by trained podiatrists on three occasions to measure the study variables: at the start of the walk (km 0), at the end of the asphalt section (half way; km 14.5) and at the end (km 29.6). The protocol of measures was followed (supplementary data).

3. Study design, route description and participants

Weight (kg)

A clinical trial randomized, double blinded was designed to analyze the influence of different types of socks (technical and non-technical) on the appearance of foot injuries after a low-difficulty, short-term sport activity. The study follow the CONSORT criteria.

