To carry out the study, the hiker was previously registered. The researchers contacted the participants to explain the study. In addition, data on age, sex, foot number and associated diseases that prevented the completion of the route were obtained. One hour before starting the route, researchers who did not intervene in the exploration process, made registration and delivery to each hiker of two technical socks (1 Set and 1 Tierra) appropriate to the size of the foot and randomly for the right foot (RF) and left foot (LF). Likewise, it proceeded for non-technical socks (cotton), but in this case both feet wore the same type of sock. All the participants before the initial exploration had their socks put on for half an hour. The hike was low-difficulty, over a short distance [37]. The first 14.5 km were on asphalt and the last 15.1 km on dirt. The height range was 189 m and the pace was moderate, at 5 km/hour. The sample comprised 109 participants (53 men and 56 women). Two women had to give up the hike for personal reasons. Both wore technical socks.

The Table 1 explain the anthropometric characteristics of the participants and the distribution of the socks, differentiating by sex and feet.

Anthropometric variable	Total	Male	Female	
Gender		48.6%	51.4%	
Age (years)	44± 25	49± 21	36 ± 24	
Height (meters)	1.7± 0.1	1.7± 0.1	1.6± 0.1	

81.0±13.5

61.4±7.8

68.8±19.4

Table 1. Anthropometric variables, total sock distribution and sock distribution by gender.

BM	II	24.9± 3.6	26.6± 3.7	23.5± 9.1
Sock type di	istribution	Total %	Male %	Female %
LF sock	Tierra	40.4 (n=44)	35.8 (n=19)	44.6 (n=25)
	Set	29.4 (n=32)	35.8 (n=19)	23.3 (n=13)
	Cotton	30.2 (n=33)	28.4 (n=15)	32.1 (n=18)
RF sock	Tierra	29.4 (n=32)	35.8 (n=19)	23.3 (n=13)
	Set	40.4 (n=44)	35.8 (n=19)	44.6 (n=25)
	Cotton	30.2 (n=33)	28.4 (n=15)	32.1 (n=18)

Km=Kilometres, n=sample size, %=Percentage, ±=Standard deviation, kg=Kilogrammes, BMI=Body mass index, LF=Left foot, RF=Right foot.

4. Study variables

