None of the other dermal lesions included in the evaluation (reddened skin, urticaria, crevice and heloma) were detected. Significant differences were found between the percentage of dermal lesions in hikers wearing technical socks (6.6%) and non-technical socks (36.4%) (p-value=0.000). The women had a higher percentage of dermal lesions (23.2%) than the men (7.5%) (p-value=0.034), regardless of sock type. Moreover, the percentage of women with dermal lesions was significantly higher among wearers of non-technical socks (50%) than in wearers of technical socks (10.5% had lesion) (p-value=0.002). Particularly the women presented more blisters in both RF and LF when they wore cotton sock compared to the Tierra and Set socks (RF p-value = 0.050, LF p-value = 0.042). In the case of men, there was no difference in any of the skin lesions at 14.5 km on any foot compared to the sock used (Table 3). The most frequent muscle lesions at the end of the first part of the hike were pain due inadequate warm (21.1%), inflammation (2.8%) and muscle discomfort (1.8%). No sprains or nail disorders were detected at the end of the first part of the hike. No difference between any of muscle lesions analyzed and technical and non-technical socks were found. By sex, no differences were found regarding technical and non-technical socks or concerning the model used sock on each foot (Table 3).

Table 4. Prevalence of skin, muscle and nail lesions during the 14.5-29.6 km of the hike by sex.

(14.5-29.6 km)				Fema	ale					N	I ale		
(14.5-29.6 KM)		Tie	rra %	Set	%	Cott	on %	Tier	ra %	Se	et %	Cott	on %
Skin lesion	%Tt.	RF	LF	RF	LF	RF	LF	RF	LF	RF	LF	RF	LF
Blister	19.6	7.7	12.0	20.0	7.7	25.0	12.5	5.3	0.0	5.3	21.1	6.7	0.0
Erosion	7.5	0.0	4.0	8.0	0.0	12.5	18.8	0.0	0.0	0.0	0.0	20.0	13.3
Reddened skin	3.7	0.0	0.0	0.0	0.0	18.8	18.8	0.0	0.0	0.0	0.0	6.7	6.7
Urticaria	0.9	0.0	0.0	0.0	0.0	6.3	6.3	0.0	0.0	0.0	0.0	0.0	0.0
Crevice	0.9	0.0	0.0	0.0	0.0	0.0	0.0	0.0	0.0	0.0	0.0	6.7	0.0
Heloma	0.9	0.0	0.0	0.0	0.0	0.0	0.0	0.0	0.0	0.0	0.0	6.7	6.7
(14.5-29.6 km)			Female			Male							

		Tier	ra %	Set	t %	Cott	on %	Tier	a %	Se	et %	Cott	on %
Muscle lesion	%Tt.	RF	LF	RF	LF	RF	LF	RF	LF	RF	LF	RF	LF
Pain due inadequate warm	11.2	15.4	4.0	4.0	7.7	0.0	12.5	10.5	0.0	5.3	10.5	0.0	0.0
Inflammation	0.9	0.0	4.0	4.0	0.0	0.0	0.0	0.0	0.0	0.0	0.0	0.0	0.0
Muscle discomfort	0.9	0.0	0.0	0.0	0.0	0.0	0.0	0.0	0.0	5.3	0.0	0.0	0.0
Sprain	0.9	0.0	0.0	4.0	0.0	0.0	0.0	0.0	0.0	0.0	0.0	0.0	0.0
(14.5-29.6 km)				Fem	ale					N	Iale		

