(14.5-29.0 KIII)		Tier	ra %	Set	t %	Cott	on %	Tierr	a %	Se	et %	Cott	on %
Nail lesion	%Tt.	RF	LF	RF	LF	RF	LF	RF	LF	RF	LF	RF	LF
Onychocryptosis	0.9	7.7	0.0	0.0	0.0	0.0	0.0	0.0	0.0	0.0	0.0	0.0	0.0
Subungual hematoma	1.9	0.0	0.0	0.0	0.0	6.3	6.3	0.0	0.0	0.0	0.0	6.7	6.7

Km=Kilometres, %=Percentage, Tt=Total, RF=Right foot, LF=Left foot.

In the second part of the hike, a greater variety of dermal lesions was detected. The most prevalent were blisters, erosions and reddened skin. Again, no urticaria, reddened skin, crevices, or helomas were detected with either technical sock. Differences were found between the percentage of dermal lesions among hikers wearing technical socks (21.1%) or non-technical socks (54.8%) (p-value=0.001). By gender, the percentage of women and men with dermal lesions was higher among wears of non-technical socks (women 68.8% and men 40%) than among wearers of technical socks (women 26.3% and men 15.8%) but the differences only were significant in women (p-value=0.006). Considering the sock used in each foot, in the case of women, presented more reddened skin in both RF and LF if they used cotton sock compared to the Tierra and Set (RF and LF p-values=0.023). In the case of men, they presented more blisters in the LF if they used Set sock than cotton or Tierra (p-value=0.021) and more erosion in the RF if they used cotton sock in comparison with the Tierra or Set (p-value=0.018) (Table 4). A greater variety of total muscle lesions was also detected in the second part of the hike: pain due to inadequate warm, inflammation, muscle discomfort and sprain. No differences were found between any of the muscular injuries analysed and the technical and non-technical socks neither by sex (Table 4).

Nail lesions like onychocryptosis (0.9%) and subungual hematomas (1.9%) were infrequently and developed only in the second part of the hike. No difference between any of the nail lesions analyzed and technical and non-technical socks were found. By sex, no differences were found (Table 4).

The temperature comparisons between technical and non-technical socks, regardless of distance, foot, measurement area and sex, showed significant differences. The Friedman test was performed (p value <0.005) for the comparisons between paired samples and the Kruskal-Wallis test was performed (p value <0.009) for independent samples. (Supplementary data, tables A, B).

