The study of the perimeter of hikers' feet analysed in total and by gender, in relation to distance and sock type, did not reveal significant results (data not shown).

Table 7. Probability of suffering skin and muscle lesions in relation to anthropometric variables and sock type throughout the hike.

1	PROBABILITY SKI	N LESIONS	PROBABILITY M	USCLE LESIONS		
Dist	ance:	Distance: 14.5-29.6 Km	Distance: 0-14.5 Km			
96% If	female	90% If male	100% I	f male		
100% If non-	technical sock	100% If non-technical sock	67% If non-te	chnical sock		
Direct relation	Inverse relation	Inverse relation	Direct relation	Inverse relation		
BMI	Age	Age	BMI	Age		

km=Kilometre, %= Percentages, BMI=Body mass index.

It was possible to study the relation between variables and predict the probability of lesions developing during the hike using logistic regression analysis (Table 7). Women have a higher probability than men of suffering skin lesions in hikes of up to 14.5 km. However, men have a higher probability than women of suffering skin lesions on hikes of 14.5 to 29.6 km and muscle lesions on hikes of up to 14.5 km.

The non-technical socks showed the highest probability of wearers suffering dermal and muscle lesions, both from 0-14.5 km and from 14.5 km to the end of the hike. The probability of dermal and muscle lesions developing in relation to the quantitative variables showed direct and inverse relations. From 0-14.5 km, the BMI and age of hikers are directly and inversely related, respectively, both in dermal and in muscle lesions. In the second part of the hike, age continued to show an inverse relation with skin lesions, but no relation with BMI was identified (Table 7).

Supplementary data

Protocol of Measures. Top shows the protocol of measure at the starting point (0 km). Middle part includes the protocol of the first part of the hike (0-14.5 km) and lower part of the table reflex the measurement protocol of the second part of the hike (14.5-29.6 km)

PPOTOCOI	OF MEASURES
STARTING POINT (0 Km)	OF MEASURES
Dorsal Number: Gender: Gender:	Foot size Weight Size
Body mass index (BMI):	The state of the s
	Previous Alterations on skin, muscles or
nails	
	rature LF
Plantar Plantar	
Dorsal Dorsal	
Perimeters RF: (Three different measures)	Perimeters LF: (Three different measures)
tibia	tibia
hell	hell
toes instep	toes instep
FIRST PART OF THE HIKE (0-14.5 Km)	Perimeters RF: (Three different measures)
	tibia
Temperature RF: (Three different measures)	
Plantar	

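### The technical-versus-cotton comparison is called randomised, but how hikers were assigned to it is not described, and it is reported unadjusted without age or BMI by sock group

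*Combined protocol and SAP*

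**What the plan says.** Section 3 gives the design and its target contrast in one sentence: "A clinical trial randomized, double blinded was designed to analyze the influence of different types of socks (technical and non-technical"). It adds that CONSORT criteria were followed.

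The same section then describes allocation. One hour before the start, researchers who took no part in the examinations gave technical hikers "two technical socks (1 Set and 1 Tierra) appropriate to the size of the foot and randomly for the right foot (RF) and left foot". For the comparison group it says: "Likewise, it proceeded for non-technical socks (cotton), but in this case both feet wore the same type of sock". It gives no sequence, ratio or concealment method, and no rule for who received cotton.

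The sample is given as "The sample comprised 109 participants (53 men and 56 women"). The baseline table is titled "Table 1. Anthropometric variables, total sock distribution and sock distribution by gender". It shows age, height, weight and BMI for the total and by sex, and counts of sock type by sex and foot.

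The Results compare hikers. For the first part of the hike they give "dermal lesions in hikers wearing technical socks (6.6%) and non-technical socks (36.4%) (p-value=0.000"). For the second part they give "dermal lesions among hikers wearing technical socks (21.1%) or non-technical socks (54.8%) (p-value=0.001"). Section 6 names chi-square or Fisher's exact test for such variables. It also mentions logistic regression quantified by odds ratios. The text with Table 7 reports that over the first 14.5 km "the BMI and age of hikers are directly and inversely related, respectively, both in dermal and in muscle lesions", and that age stays inversely related to skin lesions in the second part.

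**The concern.** The word for random allocation is attached to the left/right placement of Set and Tierra within a technical hiker. A cotton hiker wears the same sock on both feet, so nothing is left to randomise by foot. The sentence on cotton therefore does not say how that hiker came to be in the cotton group. The described randomisation supports Tierra against Set. The main claim is technical against cotton, which is a comparison between hikers.

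This matters because random assignment of hikers is what would justify reading a crude chi-square or Fisher test causally. Without a description of it, a reader would turn to baseline comparability, and the two quantitative characteristics that the document itself relates to lesions are not shown by sock group. A reader would next look for an adjusted estimate, and Table 7 gives only percentages and directions. At stake is whether the study's central conclusion may be stated as a randomised effect, and how large that effect is.

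**Working it through.** **1. Group sizes (Table 1).** Every technical hiker wears one Tierra and one Set sock, so technical hikers = left-foot Tierra + left-foot Set = 44 + 32 = 76 (men 19 + 19 = 38; women 25 + 13 = 38). Cotton hikers = 33 (15 men, 18 women). Total 76 + 33 = 109, as stated.

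**2. Reproducing the main results.** Counts are rebuilt from the percentages; two-sided tests are assumed because sidedness is not stated.
- 0–14.5 km: 5/76 = 6.6% and 12/33 = 36.4%. Fisher p = 0.0002, consistent with the printed 0.000. Events: 5 + 12 = 17.
- 14.5–29.6 km: 16/76 = 21.1% and 17/31 = 54.8%. Fisher p = 0.001, as printed.

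The arithmetic is therefore sound. The issue is interpretation. One caveat applies to the second part: the percentages need denominators of 76 and 31, which puts both withdrawals in cotton, whereas Section 3 says that both wore technical socks. With 74 technical hikers, 21.1% cannot be obtained (15/74 = 20.3%; 16/74 = 21.6%).

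**3. Crude odds ratios, cotton against technical.** OR = (events × non-events in the other group) / (the reverse); 95% CI from exp(ln OR ± 1.96 × √(1/a + 1/b + 1/c + 1/d)).
- First part: (12 × 71)/(21 × 5) = 852/105 = 8.1 (2.6 to 25.7).
- Second part: (17 × 60)/(14 × 16) = 1020/224 = 4.6 (1.9 to 11.2).

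**4. Sex, the one covariate that can be checked.** Men: 38/76 = 50.0% of technical and 15/33 = 45.5% of cotton hikers; chi-square p = 0.66. The Mantel-Haenszel odds ratio uses counts by sex rebuilt from the Results.
- First part: men 1/38 and 3/15; women 4/38 and 9/18. Numerator 3×37/53 + 9×34/56 = 2.094 + 5.464 = 7.559. Denominator 12×1/53 + 9×4/56 = 0.226 + 0.643 = 0.869. OR = 8.7, against 8.1 crude.
- Second part: men 6/38 and 6/15; women 10/38 and 11/16. Numerator 6×32/53 + 11×28/54 = 3.623 + 5.704 = 9.326. Denominator 9×6/53 + 5×10/54 = 1.019 + 0.926 = 1.945. OR = 4.8, against 4.6 crude.

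Sex does not explain the difference.

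**5. Age and BMI.** Balance by sock group cannot be computed from the document. Even under true random assignment, chance alone allows a standardised difference of 1.96 × √(1/76 + 1/33) = 1.96 × 0.208 = 0.41 SD (95% range). Taking the total-sample ± figures at face value as SDs, that is 0.41 × 25 = about 10 years of age, or 0.41 × 3.6 = about 1.5 BMI units. The table by sock group is needed whichever way assignment was done.

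**6. The split.** An exact binomial test of 76/109 against 2/3 gives p = 0.54, so the split is compatible with 2:1. No ratio is stated to compare it with.

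**The case against.** The strongest reply is that the document does call the trial randomised for technical against non-technical socks, and claims CONSORT. The sentence on cotton can be read as the same delivery process with one exception, that both feet match. Silence about a mechanism is not evidence against one. This stands: the gap is in description, and the reading that hikers were randomised remains open. It still supplies no method or ratio for hikers.

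A reader might go further and infer that the unequal split, or the equal number of technical men and women, shows that hikers were not randomised, or that cotton went to whoever was left. The document does not support that. No 1:1 ratio was ever claimed. The split fits 2:1, which would also give roughly equal numbers of feet per sock (76 Tierra, 76 Set, 66 cotton). The 38 and 38 are unremarkable under chance assignment. Nothing says that arrival time, shoe size or supply decided who got cotton. The staff who delivered socks took no part in the examinations, and it is not stated that they were the same people who had collected age, sex and foot size.

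Second, the logistic regression involves sex, sock type, age and BMI, so some adjustment may already exist. That is fair. With no model, odds ratio or interval shown, however, it cannot serve as the adjusted result.

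Third, the effect is large. The risk ratios are 36.4/6.6 = 5.5 and 54.8/21.1 = 2.6. By the E-value formula RR + √(RR × (RR − 1)), an unmeasured factor would need associations of about 10.5 and 4.6 with both sock group and lesions to remove them entirely, or 3.7 and 2.4 to bring the lower confidence limits (2.1 and 1.5) to one. This makes it less likely that confounding explains the whole difference. It does not settle the size of the effect, which is imprecise, or justify the randomised label.

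Finally, a model with four terms is unstable with 17 first-part events. That is correct, and it shapes the fix.

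**Conclusion.** The point holds as a gap in the stated basis for the central claim. The document labels technical against cotton as randomised, describes randomisation only for Tierra and Set by foot, reports the main lesion comparisons unadjusted, and does not show age or BMI by sock group. It does not establish that assignment was non-random, or that the groups were unbalanced; sex, the one covariate that can be checked, is balanced and does not move the odds ratios materially.

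The results affected are 6.6% against 36.4% (crude odds ratio about 8.1) and 21.1% against 54.8% (about 4.6). The size of any confounding by age or BMI is unknown; a small shift is more likely than a reversal. The figures rest on counts rebuilt from rounded percentages, on two-sided tests, and for the second part on the denominators that the percentages imply.

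**What to change.** 1. Add columns to Table 1 for technical and cotton hikers with age, BMI and foot size. Sex by sock group is already there.
2. Beside the crude comparison for each part of the hike, report the technical-versus-cotton odds ratio with its 95% confidence interval, adjusted for sex, age and BMI, and state the model. For the first part, with 17 events, use a penalised (for example Firth) or similarly stable fit.
3. State from the allocation record how each hiker was assigned to technical or cotton, and at what ratio. If the record does not show chance assignment, restrict the word randomised to the Tierra/Set foot placement and describe technical against cotton as a non-randomised, adjusted comparison.

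The cost is one descriptive table and one model per part of the hike, from data already collected. The intervals will probably widen, the estimate may shift a little, and the randomisation claim may narrow.

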The qualitative variables analysed were: gender, body mass index (BMI) by rank, sock type, dermal lesions (all lesions developed during the hike, both keratopathies with keratinisation disorder and dermatopathies without keratinisation disorder), muscle lesions (all lesions developed during the hike) and nail lesions (all nail lesions developed during the hike, both traumatic and non-traumatic onychopathies). The height and weight data obtained were used to calculate BMI by rank, interpreted according to the World Health Organization classification [41] (Table 2).

Table 2. Qualitative variables and categories. BMI= Body mass index.

Qualitative variable	Category	
Gender	Male Female	
BMI	Underweight (<18.5) Normal weight (18.5-24.99) Overweight (25.0-29.9) Obese ((>30)
Sock type	Technical (Tierra) Technical (Set) Non-technical (Cotton)	
Skin lesion	Blister Injury (Erosion & chafing) Reddened skin Urticaria Crevice H	Ieloma
Muscle lesion	Pain due inadequate warm Inflammation Muscle discomfort Sprain	
Nail lesion	Onychocryptosis Subungueal hematoma	

The quantitative variables analysed were: age, body mass index (BMI), temperature of each foot measured in two aspects (plantar and dorsal), and perimeter of each foot, measured in four areas (dorsal aspect of toes, instep, heel, tibia).

5. Measuring instruments

The height range and the pace hikers was controlled with a Garmin ETREX 20X GPS (Global Positioning System). Perimeter was measured with a flexible, non-elastic tape measure (Lawton 18-0160, precision 1 mm). Weight was measured using scales (Tanita UM-076, precision 0.1kg) and height was measured using the weight rod of different scales (SECA 704, precision 1 mm).

Temperatures were taken with an infrared thermometer (FTN Medisana, precision 0.18° C), calculating the mean of the three measurements. An intra rate of the measure was done to detect the error of the measure of the temperature, obtaining an error of 0.1452.

6. Statistical tests

The data were analysed using IBM SPSS Statistics for Windows, Version 22.0 (IBM, Armonk, New York). The statistical treatment consisted of data study and cleansing, descriptive variable analysis, normality test (Shapiro-Wilks test). The studies of normality were no significant (p-values between 0.000 y 0.044).

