Quantitative variables depending on whether the samples were paired or independent, Friedman's test for related samples and Kruskal-Wallis was performed for independent samples, both with Bonferroni correction for multiple testing was applied. For the qualitative variables the

chi-square or Fisher's exact test with a significance level of α = 0.05 was carried out. The variables analysed by logistic regression were quantified using the ODDS Ratio (OR). The effect size for the different variables was also calculated. First, for Kruskall-Wallis tests, the variation was between 0.443 y 0.888, and for Friedman tests, the variation was between 0.336 y 0.623. Therefore, in both cases the effect size could be considered median and high.

All p-values = 0.000 are less than 1 per 1000.

Results

After completing the first part of the hike, the most frequent dermal lesions among participants were blisters and erosions.

Table 3. Prevalence of skin, muscle and nail lesions during the 0-14.5 km of the hike by sex.

(0.14 = 1)				Fen	nale					Ma	ıle		
(0-14.5 km)		Tier	ra %	Se	et %	Cott	on %	Tier	ra %	Set	%	Cott	on %
Skin lesion	%Tt.	RF	LF	RF	LF	RF	LF	RF	LF	RF	LF	RF	LF
Blister	12.8	0.0	4.0	8.0	7.7	22.2	27.8	0.0	5.3	5.3	0.0	6.7	13.3
Erosion	2.8	0.0	0.0	0.0	0.0	11.1	5.6	0.0	0.0	0.0	0.0	6.7	0.0
(0.44.5.1)				Fer	male					Ma	ıle		
(0-14.5 km)		Tier	ra %	Se	et %	Cott	on %	Tier	ra %	Set	%	Cott	on %
Muscle lesion	%Tt.	RF	LF	RF	LF	RF	LF	RF	LF	RF	LF	RF	LF
Pain due inadequate warm	21.1	23.1	27.8	8.0	7.7	27.8	27.8	10.5	15.8	10.5	0.0	13.3	13.3
Inflammation	2.8	0.0	4.2	4.0	0.0	0.0	0.0	0.0	10.5	10.5	0.0	0.0	0.0
Muscle discomfort	1.8	0.0	0.0	0.0	0.00	0.0	0.0	5.3	5.3	0.0	0.0	0.0	0.0

Km=Kilometres, %=Percentage, Tt=Total, RF=Right foot, LF=Left foot.

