The differences in temperature are greater at the beginning of the hike than at the end. An increase in temperature from 0 km to 14.5 km was observed, and temperature stabilization of 14.5 km to 29.6 km in all types of socks. However, the increase in temperature, from the beginning to the end of the hike, varies between the types of socks in all the areas measured at the foot of the walkers; being superior when using non-technical socks (about 8.5°C) than in the case of using technical socks (about 1.2°C) (Supplementary data, tables A, B).

Table 5. Women's foot temperature by sock type.

					FEMAL	E			
Distance	Sock P-value sock			P-	value distanc	e			
(km)	Т	S	С	T-S	T-C	S-C	T	S	С
				Dor	sal temp (°C) RF			
0	34.7	35.0	19.9	1.000	0.000*	0.000*	(1)=0.002*	(1)=0.000*	(1)=0.001*
14.5	36.2	36.3	31.8	1.000	0.013*	0.000*	(2)=0.000*	(2)=0.000*	(2)=0.000*
29.6	36.3	36.3	30.6	1.000	0.000*	0.000*	(3)=1.000	(3)=1.000	(3)=0.867
				Dor	sal temp (°C) LF			
0	35.0	35.0	19.9	1.000	0.000*	0.000*	(1)=0.000*	(1)=0.005*	(1)=0.003*

14.5	36.4	36.2	32.2	0.931	0.002*	0.036*	(2)=0.000*	(2)=0.001*	(2)=0.000*
29.6	36.3	36.3	30.8	1.000	0.000*	0.000*	(3)=1.000	(3)=1.000	(3)=0.472
				Plan	tar temp ((ºC) RF			
0	34.8	34.8	20.5	1.000	0.000*	0.000*	(1)=0.007*	(1)=0.000*	(1)=0.000*
14.5	36.0	36.2	29.7	1.000	0.000*	0.000*	(2)=0.001*	(2)=0.000*	(2)=0.000*
29.6	36.2	36.2	30.6	1.000	0.000*	0.000*	(3)=1.000	(3)=1.000	(3)=1.000
				Plan	tar temp	(ºC) LF			
0	34.8	34.9	21.0	1.000	0.000*	0.000*	(1)=0.002*	(1)=0.009*	(1)=0.000*
14.5	36.2	36.0	30.2	0.287	0.000*	0.000*	(2)=0.000*	(2)=0.000*	(2)=0.000*
29.6	36.1	36.0	30.2	1.000	0.000*	0.000*	(3)=0.420	(3)=0.785	(3)=1.000

Km=Kilometres, T=Tierra, S=Set, C=Cotton, Temp=Temperature, (°C)=Degrees centigrade, RF=Right foot, LF=Left foot, (*)=Significant difference, (1)= Distance between 0-14.5 Km, (2)= Distance between 0-29.6 Km, (3)= Distance between 14.5-29.6 Km.

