By gender, no significant differences were detected between technical socks models nor in women (p-values> 0.287) nor in men (p-values> 0.249). However, significant differences were detected between each model of technical socks and the non-technical sock for all distances and areas of the feet measured (Tierra-Cotton p-values<0.013 in women and p-value<0.036 in men) and (Set-Cotton p-values<0.036 in women and p-value<0.014 in men). Regarding the distance in both men and women, differences were observed from the beginning to the end and from the beginning to the middle route with all the models. In addition, in the case of men the tendency is observed in the plant of both feet to increase the temperature from the middle to the end of the hike (LF p-value=0.056, RF p-value=0.091) although it cannot be considered statistical significance (tables 5 and 6).

Table 6. Men's foot temperature by sock type.

					MAL	.E			
Distanc		Sock		P	-value sock]	P-value dista	nce
e (km)	T	S	С	T-S	T-C	S-C	Т	S	С
]	Dorsal temp	(°C) RF			
0	34.	35.1	22.0	1.000	0.000*	0.000*	(1)=0.005	(1)=0.017	(1)=0.003*
	9						*	*	
14.5	35.	36.1	32.9	1.000	0.030*	0.014*	(2)=0.000	(2)=0.000	(2)=0.000*
	9						*	*	
29.6	36.	36.4	30.0	1.000	0.000*	0.000*	(3)=0.470	(3)=0.223	(3)=0.896
	3								
]	Dorsal tem	p (ºC) LF			
0	35.	35.3	21.4	1.000	0.000*	0.000*	(1)=0.008	(1)=0.240	(1)=0.003*
	2						*		
14.5	36.	36.0	32.5	0.931	0.036*	0.002*	(2)=0.000	(2)=0.003	(2)=0.000*
	3						*	*	
29.6	36.	36.4	30.8	1.000	0.000*	0.000*	(3)=0.128	(3)=0.401	(3)=0.558
	5								
				I	Plantar tem	p (ºC) RF			
0	34.	35.1	22.0	1.000	0.000*	0.000*	(1)=0.011	(1)=0.017	(1)=0.004*
	9						*	*	
14.5	35.	36.4	30.3	0.249	0.007*	0.000*	(2)=0.000	(2)=0.000	(2)=0.001*
	8						*	*	
29.6	36.	36.4	29.0	1.000	0.000*	0.000*	(3)=0.091	(3)=0.223	(3)=1.000
	2								
				I	Plantar tem	p (ºC) LF			
0	35.	34.9	21.8	1.000	0.000*	0.000*	(1)=0.006	(1)=0.001	(1)=0.042*
	0						*	*	

14.5	36. 1	35.7	31.2	0.287	0.000*	0.000*	(2)=0.000	(2)=0.000	(2)=0.000*
29.6	36.	36.2	29.3	1.000	0.000*	0.000*	(3)=0.056	(3)=0.401	(3)=0.558

Km=Kilometres, T=Tierra, S=Set, C=Cotton, Dif.=Difference Temp=Temperature, (${}^{\circ}$ C)=Degrees centigrade, RF=Right foot, LF=Left foot, (*)=Significant difference, (1)= Distance between 0-14.5 Km, (2)= Distance between 0-29.6 Km, (3)= Distance between 14.5-29.6 Km.

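### The 14.5 vs 29.6 km temperature p-values fit a test that treats km 0 as exchangeable with both later readings; in men's Tierra plantar cells this alone makes the late rise non-significant

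*Combined protocol and SAP*

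**What the plan says.** Section 6 (Statistical tests) gives the software as "IBM SPSS Statistics for Windows, Version 22.0" and the method for temperature as "Friedman's test for related samples and Kruskal-Wallis was performed for independent samples, both with Bonferroni correction for multiple testing was applied". It names no pairwise procedure after Friedman and no separate test for two distances. The "significance level of α = 0.05" is attached to the qualitative tests; I assume that it also governs temperature.

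Tables 5, 6, A and B print three within-sock p-values per cell: (1) 0 vs 14.5 km, (2) 0 vs 29.6 km and (3) 14.5 vs 29.6 km.

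Two statements in the Results concern comparison (3):
- The first describes "temperature stabilization of 14.5 km to 29.6 km in all types of socks".
- The second reports a tendency for men's plantar temperature to rise from the middle to the end: "LF p-value=0.056, RF p-value=0.091) although it cannot be considered statistical significance". In Table 6 these two p-values stand in the Tierra column.

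**The concern.** Comparison (3) is read as a test of whether temperature differs between 14.5 and 29.6 km. If its standard error comes from all three distances being interchangeable, it answers another question. The tables themselves reject that null, since km 0 is well below both later readings and nearly all of (1) and (2) are significant.

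Once km 0 is known to be lowest, the two later ranks can differ only by one place (or tie). The three-way standard error is then too large, and real late changes are too easily declared non-significant. At stake is the printed conclusion on the men's plantar rise, and any use of the (3) column as support for stable temperature in the second half.

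**Working it through.** **Inputs.** p-values from Tables 6, A and B; group sizes from Table 1 (19 men in Tierra on each foot). I take the tests as two-sided. D1, D2 and D3 are the rank-sum differences for comparisons (1), (2) and (3), with D2 = D1 + D3.

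**Step 1: reproduce the printed values.** Try p = 3 × 2 × [1 − Φ(|D|/√(2n))]. A search over n = 12 to 19 and all half-integer rank sums gives one solution per cell.

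| Men, Tierra, plantar | n | D1 → p(1) | D2 → p(2) | D3 → p(3) |
|---|---|---|---|---|
| LF | 19 | 19/√38 = 3.08 → 0.006 | 33.5/√38 = 5.43 → 0.000 | 14.5/√38 = 2.35 → 0.056 |
| RF | 18 | 17.5/6 = 2.92 → 0.011 | 30.5/6 = 5.08 → 0.000 | 13/6 = 2.17 → 0.091 |

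All six match Table 6. As a cross-check on dorsal RF, Table B Tierra (n = 30, D3 = 10.5, p = 0.526) and Set (n = 42, D3 = 15, p = 0.305) add up to Table A technical: n = 72, D3 = 25.5, z = 25.5/12 = 2.125, p = 0.101, as printed.

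**Step 2: how often is km 0 lowest?** The three rank sums total 6n, so the km 0 rank sum is R0 = (6n − 2·D1 − D3)/3.
- LF: (114 − 38 − 14.5)/3 = 20.5, which is 1.5 above the minimum of 19.
- RF: (108 − 35 − 13)/3 = 20, which is 2 above the minimum of 18.

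Each hiker whose km 0 reading is not strictly lowest adds at least 0.5. So this applies to at most 3 of 19 (LF) and 4 of 18 (RF).

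**Step 3: the variance.** If all three distances are exchangeable, the two later ranks differ by ±1 with probability 2/3 and by ±2 with probability 1/3. The variance per hiker is 2/3 × 1 + 1/3 × 4 = 2, the value in √(2n). If km 0 is always lowest, the difference is ±1 and the variance is 1. If km 0 lies between the other two in a fraction f of hikers, the variance is 1 + 3f.

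**Step 4: the true error rate.** The Bonferroni threshold is 0.05/3 = 1.67%, or |z| ≥ 2.394. With km 0 always lowest and no ties:
- n = 18: |D3| must reach 2.394 × 6 = 14.4, so at least 17 of 18 hikers must move the same way. The probability is 2(1 + 18)/2^18 = 0.014%.
- n = 19: |D3| must reach 2.394 × √38 = 14.8, so at least 17 of 19. The probability is 2(1 + 19 + 171)/2^19 = 0.073%.

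Simulation with a km 0 mean rank of 1.08, close to these cells (20.5/19 = 1.08 and 20/18 = 1.11), gives about 0.1% to 0.2%.

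**Step 5: the same statistic under the right null.** I listed every set of within-hiker rank orders, ties included, that matches the recovered rank sums. For each I exchanged only the 14.5 and 29.6 km labels (exact sign-flip distribution of D3) and kept the factor 3. The exact sign test is shown beside it.

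| Cell | Printed | Sign-flip × 3 | Sign test × 3 |
|---|---|---|---|
| LF | 0.056 | 0.0004 to 0.010 | 0.0004 to 0.013 |
| RF | 0.091 | 0.0007 to 0.028 | 0.0007 to 0.038 |

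No compatible data set leaves either cell above 0.05.

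**Step 6: other cells, normal approximation with variance 1 + 3f.**
- Table A technical dorsal RF (n = 72, D3 = 25.5): printed 0.101; 0.008 at f = 0, 0.040 at f = 0.16, 0.0525 at f = 0.20.
- Table A technical plantar RF (n = 72, D3 = 26): printed 0.091; 0.0065, 0.035 and 0.046 at the same f.
- Table A technical plantar LF (n = 72, D3 = 19): printed 0.340; 0.075 even at f = 0.
- Women's cells printed as 1.000: this needs |D3|/√(2n) of at most 0.97, so |D3|/√n of at most 1.37. With variance 1 the adjusted p is still about 0.5 or more.

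**The case against.** The strongest objections are these.

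- **The procedure is inferred.** True, but one formula returns all three p-values in each men's Tierra plantar cell, with group sizes that fit Table 1, and Table B adds up to Table A. The match is not perfect: Table B plantar RF Tierra (0.826) was not reproduced at any n tried.
- **The bounds belong to a rank test.** This stands. A Wilcoxon signed-rank test uses the sizes of the changes, which are not printed. With 16 hikers up and 3 down (LF), its adjusted p could run from 0.0002 to 0.31; with 14 up, 3 down and 1 tied (RF), from 0.0006 to 0.57. A reader might infer that any paired test would be significant; the printed figures do not show that.
- **Km 0 is not lowest everywhere.** This stands. In men's Set dorsal LF (n = 18, D1 = 10.5, D3 = 9) the km 0 rank sum is 26, 8 above its minimum, and Table 6 prints 0.240 for comparison (1). The distortion there is much smaller.
- **The stabilisation sentence cites no p-value.** This stands. A reader might infer that it rests on the non-significant (3) column and falls with it. The text does not say so, and as a description it suits the pooled technical socks, where Table A shows late changes of 0.1 to 0.2 °C.
- **The consequence is limited.** The error is conservative, creates no false positive, and does not touch the lesion comparisons that the design section gives as the aim. The Results already report the men's tendency with its p-values.

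**Conclusion.** The point holds for men's Tierra plantar temperature on both feet. With the same rank statistic and the same factor 3, the adjusted p is at most 0.010 (LF) and 0.028 (RF), so the phrase "although it cannot be considered statistical significance" reflects the test and not the data. This rests on the inferred procedure, two-sided testing at 0.05, and a factor of 3.

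Pooled technical dorsal RF and plantar RF probably change as well, provided that km 0 lies between the later readings in fewer than about one hiker in five.

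Two stronger readings are not supported:
- **That late changes in general were wrongly dismissed.** Women's cells printed as 1.000 and pooled technical plantar LF stay non-significant.
- **That cotton dorsal LF shows a significant late change.** The recovered ranks rise after 14.5 km (D3 of +8 in women and +7 in men), while the printed temperatures fall (32.2 to 30.8 and 32.5 to 30.8). That conflict must be settled from the raw data first.

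Significance would not mean importance. The printed men's Tierra plantar RF change is 35.8 to 36.2, or 0.4 °C, and most pooled technical changes are 0.1 to 0.2 °C, against a thermometer "precision 0.18° C". Equally, a large p-value does not show stability.

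**What to change.** - For comparison (3), and for consistency (1) and (2), use a paired test on only the two distances compared: an exact sign or sign-flip test, or Wilcoxon signed-rank. Name it in section 6 and choose it without regard to the result.
- Apply the factor 3 uniformly in Tables 5, 6, A and B. At present Table A prints 0.053 for non-technical dorsal LF where Table B prints 0.158 for the same cotton group. With n = 30 and D3 = 15, the unadjusted p is 0.0528, and 3 × 0.0528 = 0.158.
- Report the median paired change with a 95% confidence interval for each comparison.
- Rewrite the sentence on men's plantar temperature from that result, and say that it concerns Tierra.
- Base any claim of stabilisation on the confidence interval lying inside a stated margin, justified against the thermometer precision, and not on non-significance.
- Check the cotton cells against the raw data before reporting a direction.

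The cost is a re-run on data already held, edits to four tables and two sentences, and a line in section 6. The downside is that some small late changes may become significant without being important, which is why the interval should be printed beside the p-value.
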